3.4 Safety Measures

Safety will be assessed using:

- Incidence of treatment-related adverse events (TEAEs)
- Incidence and severity of treatment-emergent adverse events (TEAEs)
- Incidence of serious adverse events (SAEs)
- Incidence of TEAEs and SAEs leading to discontinuation of study medication.
- Changes in blood chemistry, hematology and coagulation parameter results
- Changes in vital signs including temperature, pulse, respiratory rate, systolic and diastolic blood pressure
- Changes in physical examination results
- Changes in electrocardiogram (ECG) results

4. SAMPLE SIZE DETERMINATION AND RATIONALE

This is a randomized study with two treatment groups. The subjects will be randomized to the treatment groups (leronlimab or placebo) in a 1:1 ratio.

A total of 50 subjects will be randomized in this study. The sample size is based on clinical judgment. No statistical power calculation is used to establish the sample size for this exploratory study.

5. INTERIM ANALYSIS

There will be no interim analysis performed in this study.

6. ANALYSIS POPULATIONS

6.1 Modified Intent-to-Treat Population

The **Modified Intent-to-Treat (mITT) population** is defined as the set of subjects who have received at least one dose of study treatment (leronlimab or placebo). This population will be used as

the primary analysis population for analysis of the primary and secondary efficacy endpoints...

6.2 PP Population

The **Per Protocol** (**PP**) **population** is defined as the set of subjects who meet the mITT Population requirements and are not associated with any major protocol violations. This population will be identified before the database lock. This population will be used as the supportive analysis population for analysis of the primary and secondary efficacy endpoints.

6.3 Safety Population

The **Safety Population** will include all subjects who have received one dose of study treatment (leronlimab or placebo). This population will be used for the analysis of safety parameters or measurements.

7. DATA CONVENTION AND RELATED DEFINITIONS

7.1 Baseline Definition

For all parameters, baseline will be defined as the last available value before the randomized treatment.

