CONFIDENTIAL Page 22 of 101

symptoms fluctuated in intensity and frequency, and 70% reported new symptoms appearing at different stages of their illness. Based on textual responses and anecdotes from the support group, patients may feel better for days or weeks only to relapse into old or new symptoms soon after.

The aim of this study is to test efficacy and safety of leronlimab (PRO140) for treatment of adult patients with prolonged symptoms of Coronavirus disease 2019 (COVID-19).

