If Visit 2 (V2) takes place on the same day as the Screening Visit (V1), scheduled assessments performed under screening (V1) do not need to be repeated at V2. Subjects will be given a diary to record all symptoms daily throughout the entire treatment period starting at baseline.

Treatment Groups

IP Study Dosage **Dosing Frequency and Amount** Form concentration

Table 4-1:

Route of Drug Administration Parenteral 2 injections of PRO 140 (2 X 2 mL/inj.) PRO 140 175 mg/mLSC injection (700 mg)solution per week on opposite sides of abdomen 2 injections of placebo (2 X 2 mL/inj.) Parenteral 0 mg/mLSC injection Placebo solution per week on opposite sides of abdomen

At V2, subjects will be randomized to receive leronlimab (PRO 140) or placebo which will be administered subcutaneously weekly at V2, V4, V6, V8, V10, V12, V14, and V16.

The following assessments will be performed at V4, V6, V8, V10, V12, V14, V16, and V17(EOT): vital signs, pulse oxygen saturation, physical examination, electrocardiogram (ECG (V17 only), PROMIS® Fatigue Scale, PROMIS® Cognitive Function- Short Form 4a, PROMIS® Sleep Disturbance – Short Form 4a, Global Health Assessment (V17 only), blood sample collection for routine serum biochemical, hematologic, coagulation and urine laboratory assessments (V10 and V17). CD4+ and CD8+ T cell count and serum cytokine and chemokine levels (V10 and V17), assessment for the requirement of hospitalization and patient compliance to daily diary completion will be checked by the site staff.

Additionally, telephone or video contact visits will be performed 3 days (±1 day) after each treatment administration visit. The requirement of hospitalization and patient compliance to daily diary completion will be checked during V3, V5, V7, V9, V11, V13, and V15 via telephone.

Adverse events and concomitant medications will be monitored throughout the study.

Follow Up Period (4 weeks after EOT± 3 days)

Follow-up visit (V18) will be performed 4 weeks after the End of Treatment (EOT) visit. The following assessments will be performed at V18: vital signs, physical examination, pulse oxygen saturation, blood sample collection for immunophenotypic biomarker analysis, assessment for the requirement of hospitalization, review of adverse events and concomitant medications.

Note: During visits conducted at the study clinic, subjects and site personnel will use appropriate protective gear (e.g., masks, gloves) to prevent the spread of the infection.

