4.2.1. Visit 2 (V2)

The following assessments will be performed at the first treatment visit prior to the first treatment administration. If Visit 2 (V2) takes place on the same day as the Screening Visit (V1), scheduled assessments performed under screening (V1) do not need to be repeated at V2.

- Physical examination (see Section 7.5);
- Vital Signs (see Section 7.6),
- Pulse oxygen saturation (SpO2) (see Section 7.10);
- Clinical Symptom Score Assessment (see Section 7.14)
- PROMIS® Fatigue Scale (see Section 7.16);
- PROMIS® Cognitive Function(see Section 7.17);
- PROMIS® Sleep Disturbance (see Section 7.18);
- Collection of blood specimens (see Section 7.8) for
 - o CD4+ and CD8+ T cell count;
 - Serum cytokine and chemokine levels;
 - o CCR5 receptor occupancy;
 - o Immunophenotypic biomarker analysis.
- Urine pregnancy test, for female subjects of childbearing potential

Subjects will be randomized 1:1 via WebView CTMS system to Leronlimab (PRO 140) or Placebo (see Section 7.13).

CONFIDENTIAL Page 50 of 101

• Leronlimab (PRO 140) 700 mg or

Placebo

Leronlimab (PRO 140) or placebo will be administered subcutaneously to all subjects at a weekly dose of 700 mg. After receiving the first leronlimab (PRO 140) dose, the following assessments will be performed:

- Vital signs (see Section 7.6),
- Pulse oxygen saturation (SpO2) (see Section 7.10),
- Concomitant medications assessment (see Section 7.7),
- Review of adverse events (see Section 9)

4.2.2. Visits 3, 5, 7, 9, 11, 13, and 15 (V3, V5, V7, V9, V11, V13, and V15)

Telephone or video contact visits will be performed 3 days (± 1 day) after each treatment administration visit. The following assessments will be performed:

- Patient Symptom Diary (see Section 7.15);
 Note: Patient compliance to daily diary completion will be checked by site staff.
- Assessment for the requirement of hospitalization (see Section 7.12);
- Prior and concomitant medications assessment (see Section 7.7); and
- Review of adverse events (see Section 9).

4.2.3. Visits 4, 6, 8, 10, 12, 14, and 16 (V4, V6, V8, V10, V12, V14, and V16)

The following assessments will be performed:

- Physical examination (see Section 7.5);
- Vital Signs (see Section 7.6),
- Pulse oxygen saturation (SpO2) (see Section 7.10);
- Patient Symptom Diary (see Section 7.15);

Note: Patient compliance to daily diary completion will be checked by site staff.

- PROMIS® Fatigue Scale (see Section 7.16);
- PROMIS® Cognitive Function (See Section 7.17);

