8.2.2. Secondary Endpoints

The secondary efficacy endpoints for the study are:

• Duration of COVID-19 associated symptoms from start of study treatment (Day 0) based on self-assessment using daily symptom diary.

Duration is defined as number of days when any symptoms scored as

- moderate or severe is defined as number of days are still scored as moderate or severe (i.e., not mild or absent) through Day 56, or
- mild or absent at study entry are scored as mild or worse (i.e., not absent) through Day 56.
- Number of symptom-free days of COVID-19 associated symptoms that were present at the start of study treatment (Day 0) based on self-assessment using daily symptom diary.
 - Symptom-free days are defined as number of days when any symptoms scored as mild, moderate or severe at baseline are scored as absent (or none) through Day 56.

CONFIDENTIAL Page 68 of 101

• Progression (or worsening) of COVID-19-associated symptoms through Day 56 compared to baseline.

Progression or symptom worsening is defined as number of days when any symptoms scored as

- moderate at baseline are scored as severe through Day 56.
- mild at baseline are scored as moderate or severe through Day 56.
- absent at baseline are scored as mild, moderate or worse through Day 56.
- Change from baseline in PROMIS® Fatigue Score at Days 28 and 56.
- Change from baseline in PROMIS® Cognitive Function Score at Days 28 and 56.
- Change from baseline in PROMIS® Sleep Disturbance Score at Days 28 and 56.
- Incidence of hospitalization during the treatment phase
- Duration (days) of hospitalization during the treatment phase

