9	What was the severity of your muscle aches/cramps at its worst over the last 24 hours?	
	None = 0, $Mild = 1$, $Moderate = 2$, $Severe = 3$	
1	0. What was the severity of your muscle weakness at its worst over the last 24 hours?	
	None = 0, $Mild = 1$, $Moderate = 2$, $Severe = 3$	

CONFIDENTIAL Page 95 of 101

11. What was the severity of your joint pain/swelling at its worst over the last 24 hours?

$$None = 0$$
, $Mild = 1$, $Moderate = 2$, $Severe = 3$

12. What was the severity of your chills or shivering at its worst over the last 24 hours?

$$None = 0$$
, $Mild = 1$, $Moderate = 2$, $Severe = 3$

13. What was the severity of your feeling hot or feverish at its worst over the last 24 hours?

```
None = 0, Mild = 1, Moderate = 2, Severe = 3
```

14. What was the severity of your difficulty in concentration (brain fog) at its worst over the last 24 hours?

```
None = 0, Mild = 1, Moderate = 2, Severe = 3
```

15. What was the severity of your sleep disturbance (insomnia) at its worst over the last 24 hours?

```
None = 0, Mild = 1, Moderate = 2, Severe = 3
```

16. What was the severity of your **headache** at its worst over the last 24 hours?

```
None = 0, Mild = 1, Moderate = 2, Severe = 3
```

17. What was the severity of your dizziness at its worst over the last 24 hours?

$$None = 0$$
, $Mild = 1$, $Moderate = 2$, $Severe = 3$

18. What was the severity of your **anxiety** at its worst over the last 24 hours?

$$None = 0$$
, $Mild = 1$, $Moderate = 2$, $Severe = 3$

19. What was the severity of your feeling of tingling or numbness in at its worst over the last 24 hours?

$$None = 0$$
, $Mild = 1$, $Moderate = 2$, $Severe = 3$

20. What was the severity of your nausea (feeling like you wanted to throw up) at its worst over the last 24 hours?

```
None = 0, Mild = 1, Moderate = 2, Severe = 3
```

21. How many times did you vomit (throw up) in the last 24 hours?*

```
I did not vomit at all = 0, one or two times = 1, three or four times = 2, five or more times = 3
```

22. How many times did you have diarrhea (loose or watery stools) in the last 24 hours?*

I did not have diarrhea at all = 0, one or two times = 1, three or four times = 2, five or more times = 3

23. Rate your sense of smell in the last 24 hours

```
My sense of smell is THE SAME AS usual = 0,
My sense of smell is LESS THAN usual = 1
I have NO sense of smell = 2
```

24. Rate your sense of taste in the last 24 hours

```
My sense of taste is THE SAME AS usual = 0

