8.2.1 Primary Efficacy Endpoint

The primary endpoint for the study is changes from baseline in daily COVID-19-related symptom severity score through day 56.

Daily COVID-19 related symptom score is the sum of score from Assessment of COVID-19-related symptoms.

For this endpoint, proportions of subjects in each category will be summarized and compared using proportional odds model, adjusting for baseline COVID-19 related symptom score and stratification factors. Odds Ratio estimates and 95% Confidence Interval will also be calculated.

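### The baseline diary total rests on a single 24-hour recall although the protocol describes fluctuating symptoms; averaging the pre-dose scores would cheaply improve precision, and the day-count thresholds need a separate repair

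*Combined protocol and SAP*

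**What the plan says.** **Baseline.** SAP 7.1: "For all parameters, baseline will be defined as the last available value before the randomized treatment". No averaging rule for the diary appears elsewhere.

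**Instrument.** Each severity item in protocol Appendix 1 takes the form "What was the severity of your muscle weakness at its worst over the last 24 hours". SAP 8.2.1 builds the primary score from these items: "Daily COVID-19 related symptom score is the sum of score from Assessment of COVID-19-related symptoms".

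**Pre-dose scores.** Protocol 7.14 takes the clinical symptom score from the diary at V1 and at V2. Under SAP 7.1 only the later one becomes baseline. If both visits fall on one day, protocol 4.2.1 says that "scheduled assessments performed under screening (V1) do not need to be repeated at V2", so one recall may be the only pre-dose record.

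**Diary start.** Protocol 4 says "Subjects will be given a diary to record all symptoms daily throughout the entire treatment period starting at baseline". Protocol 7.15 instead has the diary handed out once treatment has been given. On neither reading is there a daily series during the screening week.

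**Disease.** In protocol 1.2, 89% of surveyed patients reported that their "symptoms fluctuated in intensity and frequency, and 70% reported new symptoms appearing at different stages of their illness"; the section adds that "patients may feel better for days or weeks only to relapse into old or new symptoms soon after".

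**Use of baseline.** SAP 7.5 and 8.2.1 adjust for it. In protocol 8.2.2 and SAP 3.2, each symptom's baseline class also sets how its days are counted, for example "mild at baseline are scored as moderate or severe through Day 56" for worsening.

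**The concern.** A one-day score mixes the patient's usual level with that day's deviation. The more a symptom varies, the less one day says about the usual level, the less variance the covariate removes, and the more noise enters each diary change score. The trial has 50 subjects and no power calculation (SAP 4), so precision that costs almost nothing is worth taking.

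The three diary day-count endpoints raise a different problem. There the single day is also part of the outcome definition, because it decides which counting rule applies to a symptom or whether the symptom is counted at all. Covariate adjustment cannot remove noise that has been built into the outcome.

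**Working it through.** The plan gives no figure to reproduce: the sample size is a clinical judgment, and no variance or correlation is stated for the diary score.

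**1. Total score.** The score sums 24 items, 22 scored 0-3 and 2 scored 0-2, so the maximum is 22 × 3 + 2 × 2 = 70.

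Assumptions, none of them from the documents: single-day reliability r = 0.5-0.7; correlation c = 0.7-0.8 between the underlying baseline and on-study levels; independent daily deviations; an outcome averaged over the study and treated as free of day-to-day error.

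- Reliability of a k-day mean: R = k·r / (1 + (k − 1)·r)
- ANCOVA residual variance, as a share of outcome variance: 1 − c²·R

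| r | c | 1 day | 2 days | 3 days | Fall, 2 days | Fall, 3 days |
|---|---|---|---|---|---|---|
| 0.5 | 0.7 | 0.755 | 0.673 | 0.633 | 10.8% | 16.2% |
| 0.5 | 0.8 | 0.680 | 0.573 | 0.520 | 15.7% | 23.5% |
| 0.7 | 0.7 | 0.657 | 0.596 | 0.571 | 9.2% | 13.1% |
| 0.7 | 0.8 | 0.552 | 0.473 | 0.440 | 14.3% | 20.3% |

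The ranges are therefore about 9-16% for two days and 13-24% for three.

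*Single-day outcome.* If the outcome is also one noisy day, such as Day 56, the residual share is 1 − c²·r·R. The same inputs give falls of 5-8% for two days and 7-11% for three. For example, with r = 0.7, c = 0.8 and three days, 1 − 0.608/0.686 = 11.4%.

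*Serially correlated days.* With lag-1 correlation φ, the error variance of a three-day mean is (3 + 4φ + 2φ²)/9 of the one-day value, which is 0.611 at φ = 0.5 and 0.831 at φ = 0.8. Putting this into R = r / (r + (1 − r) × factor), with the averaged outcome, the three-day fall is 7-11% at φ = 0.5 and 3-4% at φ = 0.8.

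**2. Day counts, one symptom at a time.** Take a symptom that is mild (1) or moderate (2) each day, moderate with probability p, unchanged over 56 days. SAP 3.2 counts a duration day at 2 or more if baseline was 2 or 3, and at 1 or more if baseline was 0 or 1.

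- Baseline moderate: duration 56p days, worsening 0.
- Baseline mild: duration 56 days, worsening 56p.
- Gap in duration: 56(1 − p).

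| p | Duration, moderate baseline | Duration, mild baseline | Gap | Worsening, mild baseline |
|---|---|---|---|---|
| 0.2 | 11.2 | 56 | 44.8 | 11.2 |
| 0.3 | 16.8 | 56 | 39.2 | 16.8 |
| 0.5 | 28 | 56 | 28 | 28 |
| 0.7 | 39.2 | 56 | 16.8 | 39.2 |

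The milder baseline day yields the longer duration, with no change in the patient. The duration rule switches only between 1 and 2. Entry into the symptom-free count switches only between 0 and 1. Worsening changes at every class.

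**3. Would a median baseline class cure this?** For strict mild/moderate alternation, an odd number of entries gives a median of 1 or 2 depending on the starting day, which leaves the same switch. An even number gives 1.5, for which there is no rule. The fault lies in the thresholds, not only in the number of baseline days.

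**The case against.** Using the last pre-dose value is a common convention, the trial is declared exploratory, and baseline is already a covariate. The fluctuation evidence comes from a support-group survey of patients on average at day 40, whereas this trial enrols beyond 12 weeks. All of that stands and makes this a precision improvement rather than an error.

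Four stronger readings are tempting, and the documents do not support them.

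- *The trial measures the enrolment day rather than treatment.* Randomized arms share the baseline noise and any regression to the mean, so the between-arm comparison is not biased by it.
- *Every change score is affected.* The PROMIS forms use 7-day recall (Appendices 3-5), and SpO2 and laboratory endpoints do not come from the diary.
- *Averaging is worth 60-73 subjects instead of 50.* That follows from one-day to five-day variance ratios of 1.20-1.46 (50 × 1.20 = 60; 50 × 1.46 = 73). It needs five entries, an outcome free of daily error and independent days, while relapse over days or weeks points to serial correlation. Nor does it carry over to the planned proportional odds model, whose categories are undefined.
- *Day counts are distorted for every subject.* Both documents count days when any symptoms qualify and do not say whether this is per symptom or per subject. At subject level, simulated duration (24 items, assumed correlations 0.5-0.9) averaged 55-56 of 56 days, so one symptom's switch would hardly show. That reading has its own weakness: the endpoint barely discriminates.

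**Conclusion.** The point holds as a low-cost improvement to the diary baseline. The total score used as covariate and as the reference for change is one 24-hour recall, and nothing in the plan stabilizes it. The harm is lost precision, not bias. The 9-16% (two days) and 13-24% (three days) are illustrations under the stated assumptions and sit towards the favourable end; a single-day outcome or correlated days brings them down to single figures or little above.

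The day-count problem is separate and needs no reliability assumption. On a per-symptom reading, an unchanged symptom that is moderate on half its days scores about 28 or 56 days of duration according to one baseline day. A better baseline does not remove this for borderline symptoms.

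**What to change.** **Minimum, no new data.** In SAP 7.1, define the baseline diary total as the mean of all pre-dose daily totals, so that V1 and V2 are averaged when they fall on different days. Subjects with same-day visits would keep a one-day baseline; the SAP should say so.

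**Preferred.** Issue the diary at V1 and have it completed daily through the pre-dose V2 entry, with at least three entries, inside the existing 7-day screening window. Except the diary from the same-day waiver. Reconcile protocol 4 and 7.15 on when the diary starts. Leave the V1 and V2 eligibility test (Table 4-2, note 6) as it is.

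**Day counts.** In protocol 8.2.2 and SAP 3.2 and 8.2.2, replace the class-dependent thresholds, for example by one common threshold for all baseline classes. In the half-and-half example, a common threshold of 2 gives 28 duration days, and a threshold of 1 gives 56, whichever day is baseline. State also whether days are counted per symptom or per subject.

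**Cost.** Short wording changes. The preferred version adds a few diary days per subject and gives up same-day screening and randomization.

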7.2 Duplicate Data

For unplanned duplicate data within a protocol-specified visit, all collected data will be listed and the last measured value will be used for the analysis. If it is not possible to identify the "last measured value," the average of the duplicate values will be used.

7.3 Handling of Missing Data

Every effort will be made to obtain required data at each scheduled evaluation from all subjects who have been randomized to minimize missing data. Missing data will not be imputed.

7.4 Multiple Comparisons and Type I Error Rate Multiplicity adjustments

There will be no adjustment for multiple testing or multiplicity for this phase II trial. For all effectiveness endpoints, inference will be based on type I error rate of 0.05.

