8.10.4. Efficacy Analyses

Primary Analysis

The mITT population will be the primary population for the analysis of the efficacy endpoints of the study.

Primary Endpoint

The primary endpoint for this study is the change from baseline in Fatigue Severity Score at Day 28.

Secondary Endpoints

To maintain the trial-wise Type I error rate at 0.05, a closed test procedure will be used for the secondary endpoints. The order of the secondary endpoints will be prospectively specified in the SAP.

Analysis of the secondary and exploratory endpoints will be summarized according to the variable type:

- Continuous data summaries will include:
 - o If the Normality assumption is met, Analysis of Covariance (ANCOVA) would be used.
 - If the Normality assumption is not met, a non-parametric method or a rank ANCOVA analysis i.e., an ANCOVA analysis on rank-transformed data will be used.
- Categorical data summaries will be based on Logit model will be used.
- Time-dependent data: Cox proportional hazards model will be used to analyze time dependent data and to depict the time to event data.

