3.2 Secondary Endpoints

The secondary endpoints for the study are:

• Duration of COVID-19 associated symptoms from start of study treatment (Day 0) based on self-assessment using daily symptom diary

Duration is defined as number of days when any symptoms scored as

- 2 or 3 at baseline are still scored as 2 or 3 (i.e., not 0 or 1) through Day 56, or
- 1 or 0 at study entry are scored as 1 or worse (i.e., not 0) through Day 56.
- Number of symptom-free days of COVID-19 associated symptoms that were present at the start of study treatment (Day 0) based on self-assessment using daily symptom diary *Symptom-free days are defined as number of days when any symptoms scored as* 1, 2 or 3 at baseline are still scored as 0 through Day 56.
- Progression (or worsening) of COVID-19-associated symptoms through Day 56 compared to baseline

Progression or symptom worsening is defined as number of days when any symptoms scored as

- 2 at baseline are still scored as 3 through Day 56, or
- 1 at baseline are still scored as 2 or 3 through Day 56, or
- 0 at study entry are scored as worse (i.e., not 0) through Day 56.
- Change from baseline in PROMIS® Fatigue Score at Days 28 and 56
- Change from baseline in PROMIS® Cognitive Function Score at Days 28 and 56
- Change from baseline in PROMIS® Sleep Disturbance Score at Days 28 and 56
- Incidence of hospitalization during the treatment phase
- Duration (days) of hospitalization during the treatment phase

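### The protocol claims a trial-wise type I error of 0.05 from an ordered closed test; the SAP gives no order and no adjustment, so the claim does not hold as written

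*Combined protocol and SAP*

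**What the plan says.** Protocol 8.10.4 makes two commitments. The first is the error rate and the method: "To maintain the trial-wise Type I error rate at 0.05, a closed test procedure will be used for the secondary endpoints". The second places the missing detail in the SAP: "The order of the secondary endpoints will be prospectively specified in the SAP".

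SAP 7.4 states the opposite policy: "There will be no adjustment for multiple testing or multiplicity for this phase II trial". It continues: "For all effectiveness endpoints, inference will be based on type I error rate of 0.05".

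SAP 3.2 and 8.2.2 list the secondary endpoints and their methods, with no testing sequence, stopping rule or gate. SAP 1 names protocol version 5.0 among the documents reviewed, and SAP 10 says this is the first SAP version. Nowhere does the SAP say that it departs from protocol 8.10.4.

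The documents also disagree about the primary endpoint. Protocol 8.10.4 says: "The primary endpoint for this study is the change from baseline in Fatigue Severity Score at Day 28". SAP 8.2.1 says: "The primary endpoint for the study is changes from baseline in daily COVID-19-related symptom severity score through day 56". Protocol 8.2.1 and SAP 3.1 agree with SAP 8.2.1.

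**The concern.** The two documents give opposite answers to a simple question: is a secondary p-value below 0.05 protected against multiple testing? Someone reading only the protocol would credit the secondary results with a control that the analysis does not have.

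Waiving adjustment is not in itself the fault. Both documents call the trial exploratory, and SAP 4 adds: "No statistical power calculation is used to establish the sample size for this exploratory study". The fault is to claim control in one document and waive it in the other.

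Two further gaps mean that adding an order to the SAP would not be enough. The head of any sequence is unsettled, because two different primary endpoints are named and SAP 8.2.1 fixes no single time point for the primary test. The protocol's closed test also covers only the secondary endpoints, and nothing makes the primary a gate to them.

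**Working it through.** **Inputs**

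- Stated trial-wise error: 0.05 (protocol 8.10.4).
- Per-test level under the SAP: 0.05 (SAP 7.4). Sidedness is not stated; two-sided is assumed.
- Secondary endpoints: 8 (SAP 3.2), namely three diary day-counts, three PROMIS scores, and the incidence and duration of hospitalization.
- Each PROMIS score has two time points, for example "Change from baseline in PROMIS® Fatigue Score at Days 28 and 56". Testing both days gives 3 + (3 × 2) + 2 = 11 secondary tests.
- Primary, counted once: total 1 + 11 = 12 tests, or 1 + 8 = 9 if each PROMIS score counts as one.
- Interim looks: none (SAP 5).
- Correlations between test statistics: not given, so assumed and varied.

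All figures below are the chance of at least one false positive when every null hypothesis is true.

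**1. The protocol's 0.05.** In a fixed sequence at 0.05, with every null true, a false positive requires the first test to reject. That chance is 0.05 whatever the correlation. Simulation with 400,000 draws gave 0.0496 to 0.0510 for correlations from 0 to 0.9. The stated figure is therefore attainable within the ordered family, but only with a stated order.

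**2. The SAP's rule, independent tests.** The chance is 1 − 0.95^m:

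- m = 8: 1 − 0.95^8 = 0.337
- m = 9: 1 − 0.95^9 = 0.370
- m = 11: 1 − 0.95^11 = 0.431
- m = 12: 1 − 0.95^12 = 0.460

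**3. The SAP's rule, correlated tests.** For normal test statistics with common correlation ρ and c = 1.96, the chance is

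1 − ∫ φ(g) [Φ((c − √ρ g)/√(1−ρ)) − Φ((−c − √ρ g)/√(1−ρ))]^m dg.

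| Assumed ρ | 8 tests | 9 tests | 10 tests | 11 tests | 12 tests |
|---|---|---|---|---|---|
| 0 | 0.337 | 0.370 | 0.401 | 0.431 | 0.460 |
| 0.3 | 0.300 | 0.326 | 0.351 | 0.375 | 0.397 |
| 0.5 | 0.250 | 0.269 | 0.287 | 0.304 | 0.319 |
| 0.7 | 0.191 | 0.202 | 0.213 | 0.223 | 0.232 |
| 0.9 | 0.119 | 0.124 | 0.128 | 0.131 | 0.135 |

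The 10-test column leaves out the two hospitalization tests, which can contribute little if very few subjects are admitted.

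**4. A grouped pattern.** Take groups of 4 (primary and diary counts), 6 (PROMIS) and 2 (hospitalization), with assumed correlations of 0.7 within and 0.3 between groups. Simulation gives 0.313, or 0.263 without the hospitalization group.

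**5. Is an order for the secondary endpoints enough?** With the primary tested at 0.05 and, beside it and not gated by it, a properly closed secondary family at 0.05, the chance is 1 − 0.95² = 0.0975 if the two are independent. Whatever the dependence, it is at most 0.05 + 0.05 = 0.10. A trial-wise 0.05 therefore also needs the primary as gate, or a split of alpha.

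**The case against.** The strongest reply is that the analyst is in no doubt. Protocol 8 presents itself as a short outline and leaves detailed methods to the SAP, and SAP 7.4 openly declines adjustment for a phase II trial. In an unpowered study of 50 subjects that is a defensible policy, and the damage is confined to one sentence in the protocol. This stands as a limit on the seriousness of the point. It does not remove the contradiction: the protocol left the SAP the task of supplying the order, and the SAP instead dropped the procedure while the protocol's claim remained. SAP 7.4 also speaks of inference at 0.05 and does not call the p-values nominal.

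Four narrower points are fair:

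- Twelve is a counting choice. With PROMIS counted once per score there are nine tests, and the figures fall to 37%, 27%, 20% and 12% at correlations of 0, 0.5, 0.7 and 0.9.
- Independence is unrealistic. The primary and the three day-counts come from one diary, and each PROMIS score is measured twice in the same subjects. The correlated rows are the better guide.
- How little the hospitalization tests contribute depends on the test used, which the SAP does not settle. The 10-test column is only a sensitivity case.
- The primary-endpoint conflict is a defect in its own right. It matters here because a gated sequence cannot be written until it is resolved.

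None of these brings the error rate to 0.05.

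**Conclusion.** The concern holds. The trial-wise 0.05 in protocol 8.10.4 is not delivered by the analysis in SAP 7.4, and no testing order exists from which it could be recovered. The SAP's numbered list cannot serve as an implied order, because SAP 7.4 rules out any multiplicity procedure.

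The size cannot be reduced to one number. Under the global null, with two-sided tests at 0.05 and jointly normal statistics, it runs from 46% (12 independent tests) down to 12% (8 tests at an assumed correlation of 0.9), which is still more than twice the stated rate. The conclusion depends neither on the correlation chosen nor on the count.

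This is an unsupported claim that should be corrected. It is not a reason to call the SAP's choice of unadjusted testing wrong for an exploratory trial.

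**What to change.** Before unblinding, adopt one of two routes.

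**(a) Deliver the control.** Reconcile the primary endpoint across protocol 8.10.4, protocol 8.2.1, SAP 3.1 and SAP 8.2.1, and define one primary test with its time point and method. Then state a fixed sequence in SAP 7.4: the primary as gatekeeper at two-sided 0.05, followed by the secondary tests in an order chosen by the sponsor, each at 0.05 and with one settled method, stopping at the first non-significant result. Later and exploratory p-values are nominal. The gate is an addition to the protocol text, and the trial-wise claim needs it.

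**(b) Withdraw the claim.** Keep unadjusted testing, delete the trial-wise error and closed-test sentences from protocol 8.10.4 together with the sentence on the order, and label all secondary p-values nominal in the SAP.

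Either route needs SAP text and a written protocol amendment under protocol 11.3, with no extra subjects or data. Route (b) is the shorter. Route (a) also carries the work of defining the primary test. Its price is that nothing after the first failure can be claimed: if the primary misses, all 11 secondary tests are nominal. The price of (b) is that no secondary endpoint supports an error-controlled claim.
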